4 SELECTION AND ENROLLMENT OF PARTICIPANTS

4.1 Inclusion Criteria

Women, 21 years of age and older, who desire permanent sterility and have an obstetric indication for a cesarean delivery will be included. Patients will be consented for the cesarean delivery and sterilization procedure per standard Family Birth Center guidelines. Patient with state insurance will also require correctly completed sterilization consent paperwork.

4.2 Exclusion Criteria

Pregnant women undergoing an emergent or Beta/Alpha cesarean delivery, who are not already enrolled, will not be eligible. Women who undergo tubal ligation after vaginal delivery will not be eligible. Women with a body mass index (BMI) ≥ 50 will not be eligible. Women who have a single ovary/fallopian tube will not be eligible.

4.3 Study Enrollment Procedures

Women who are 21 years of age and older and desire permanent sterility who plan to have a planned cesarean delivery will be identified as early in gestation as possible. These women will be approached for possible participation in the study during their antepartum. Most subjects will be recruited and consented in the clinic setting. Women who present to the Family Birth Center and develop an indication for a non-emergent Cesarean delivery and desire permanent sterility will be approached for participation in the study. The consents are in English, but we will use interpreter to consent women who speak other languages and are interested in participation. All women must be able to provide consent themselves for study. We will keep a record of all women who are recruited for study and record the number of women who decline.

Consenting Procedure

Women will be provided information about the study in a private exam or hospital room. Questions will be addressed and time provided to consider participation. Informed consent for the study will be obtained by study coordinator or those providers listed in the IRB, excluding the surgeon who will be performing the procedure.

The consent document will be retained by the study coordinator. During the final process to re-affirm consent for the study at the time of planned cesarean delivery, if

the patient then chooses to reverse her decision to participate, her wishes will be respected. If a patient consents to the study and then becomes ineligible (screen failure) this will be communicated with her both prior to and after the cesarean delivery.

Study Risks

The risks of a bilateral tubal ligation include bleeding from the surgical site that may require further surgery including removal of the ovary. The bleeding may also be severe enough to require a blood transfusion. The other risks include a risk of sterilization failure where one of every 100 cases results in a pregnancy for which 50% of those pregnancy results in a pregnancy in the tubes that may require further treatment. Other risks include infection and damage to surrounding organs. There may be an increased risk of pain during menses with a bilateral tubal ligation.

The risks of bilateral salpingectomy are similar to those of a bilateral tubal ligation. There may be an increased risk of bleeding compared to a bilateral tubal ligation because all of the tube is removed and therefore increased risk of need for removal of ovary and blood transfusion compared to a bilateral tubal ligation. Additionally there may be a decrease failure rate as all of the tube is removed.

There may be other risks of bilateral salpingectomy following cesarean section that are currently unknown.

5 STUDY INTERVENTIONS

5.1 Interventions, Administration, and Duration

Interventions will consist of randomization for patients desiring permanent sterilization at the time of cesarean delivery. Randomization will be to either salpingectomy or to the standard BTL arm.

The administration of the intervention will be done immediately after cesarean delivery in patients who have already been consented and enrolled in the study.

There are no medications involved in the study.

5.2 Handling of Study Interventions

There are no drugs or lifestyle/behavioral interventions in the study.

The intervention being investigated is the safety of salpingectomy as a form of sterilization vs BTL at the time of Cesarean delivery. Patients meeting enrollment criteria are those who desire permanent sterilization, are correctly consented, and are planning a repeat cesarean delivery. They will be blinded to the operative intervention at the time of

enrollment and randomization; after the surgery, it will be disclosed to them the procedure they had performed.

To investigate differences in mean hemoglobin, preoperative hemoglobin and postoperative hemoglobin will be obtained for all study participants.

To investigate the differences in operative time for the different surgical procedures being studied, all surgeries will be timed beginning at the initiation of the sterilization procedure being performed (i.e., once the cesarean delivery has been completed, and just prior to starting either the tubal ligation or salpingectomy procedure).

5.3 Concomitant Interventions

There are no medication interventions in the trial.

5.3.1 Required Interventions: If required, iron replacement for blood loss anemia and/or transfusion of blood products may be administered as standard of care.

5.3.2 Prohibited Interventions: Individuals undergoing emergency (alpha) cesarean and beta C-sections who have not previously been enrolled will not be approached for participation in this study.

5.4 Adherence Assessment

Adherence to the study regimen will be ascertained as the number of participants enrolled in the study that actually complete the procedure to which they are randomized. The study is powered for 60 patients in each arm to detect a difference in postoperative hemoglobin.

Patients will be given the right to decline either procedure if they decline permanent sterilization and voice this request prior to their planned cesarean delivery or prior to sterilization procedure.

We will incorporate into our analysis any patients who decline permanent sterilization after being enrolled in the study.

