6 STUDY PROCEDURES

Patients will be screened to be eligible in the study if they :

- 1) Desire permanent sterilization
- 2) Are scheduled for a Cesarean delivery (no emergency/'alpha' deliveries)
- 3) Are equal to or greater than 21 years of age
- 4) Have a BMI < 50

5) Have both ovaries/fallopian tubes

Patients may be screened for eligibility antenatally in the obstetrics clinic or at the time of presentation to the Family Birth Center for a non-emergent Cesarean delivery. If they meet eligibility, they will have the option to enroll in the study. A preoperative hemoglobin will be done at admission to the Family Birth center for delivery. If the patient is screened and enrolled at the time of admission to the birth center, a preoperative hemoglobin will be obtained prior to the planned cesarean delivery. All patients enrolled will have a postoperative hemoglobin obtained between 24 hours and 48 hours after the cesarean delivery and concomitant intervention procedure. Patients will be scheduled for a standard 6 weeks postpartum follow- up visit which will be reviewed. Patients who enroll in the study and then subsequently decline any form of permanent sterilization will be noted in the analysis of the results and discussed accordingly.

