6.1 Schedule of Evaluations

Assessment	Antepartum Screening Enrollment	Delivery/ Sterilization Visit 1	24-hours PP Visit 2	Follow-up: 6 Week PP
Informed Consent Form	X	*X		
Demographics	X	X		
Medical History	X	X		X
Hematology		X	X	
Inclusion/Exclusion Criteria	X	*X		
Randomization		X		
Adverse Events		X	X	X

*Patients who are screened and enrolled at the time of admission to L&D will have demographic, medical history, current medications, and vital signs reviewed/collected at the time informed consent is obtained. Patients who are screened and enrolled antenatally will at the time of admission for their planned cesarean delivery.

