6.2.2 Enrollment, Baseline, and/or Randomization

Enrollment

Patients will be considered for enrollment if they meet inclusion criteria (please refer to section 4.1). If a patient expresses a desire to undergo permanent sterilization to her provider at any time and will undergo a cesarean delivery then she is eligible for enrollment and the study coordinator will be contacted to introduce the study and obtain informed consent.

In the event the study coordinator is not available for consent (i.e., middle of the night, spontaneous onset of labor in a patient planning repeat cesarean for delivery), then an obstetrical provider listed in the IRB will be able to obtain consent for enrollment. The delivering provider will not obtain consent.

Randomization

- Initiation of study intervention relative to randomization: When patients have been enrolled in the study they will be randomized. The Dynamic Allocation System will be used for electronic randomization based on the stratification criteria. Outcome of randomization (arm) will be communicated to the surgical team prior to surgery and to the participant following surgery.
- After cesarean delivery has been performed and the surgeon feels it is safe to proceed with surgical sterilization procedure identified from randomization (salpingectomy vs BTL), the start and stop time of the surgical procedure will be recorded by the circulating RN or other obstetrical provider on a case report form. Total time of the procedure, in minutes, will be recorded.

Follow-up Visits (abstracted from the Electronic Medical Record)

- Visit 1 (24 hours post operatively)
 - Vital signs
 - Physical exam
 - Medications
 - Hemoglobin
 - Adverse events
- Visit 2: Scheduled post-partum exam 6 weeks post procedure.
 - Vital signs
 - Physical exam
 - Medications
 - Adverse events

Completion/Final Evaluation

Final visit will be at the patient's postpartum exam. Any untoward events from after the first 24 hours from the procedure to that time will be reviewed (i.e., blood transfusion, readmission to hospital, etc.). If the participant receives post-partum care at a local clinic, not Mayo Clinic Rochester, the study coordinator will call the participant to collect final evaluation data, using an IRB-approved telephone script.

Patients who decide to withdraw from the study will also be interviewed and reasons for this will be discussed and potential reasons explored.

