9 STATISTICAL CONSIDERATIONS

9.1 General Design Issues

The null hypothesis in this non-inferiority trial is that the mean difference in pre and postoperative hemoglobin of patients undergoing salpingectomy will be lower than that for patients undergoing BTL at the time of cesarean delivery by at least 0.5 g/dl. The alternative hypothesis to be proven is that this difference will be no lower than 0.5 g/dl.

A non-inferiority trial was chosen as the study aims to compare a less commonly performed procedure with a known and accepted standard. We want to show that the less common procedure is at as safe as the standard. Patients will be randomly assigned to salpingectomy or BTL at enrollment.

Primary hypothesis: The alternative hypothesis to be tested is that the mean difference in pre and postoperative hemoglobin of patients undergoing salpingectomy will be no lower than those that undergoing BTL at the time of cesarean delivery.

Primary variable: Mean hemoglobin change

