9.5 Data Analyses

A 1-sided 95% confidence interval will be constructed for the difference between study arms in the mean drop in hemoglobin. In addition, the reduction in hemoglobin will be analyzed using a one-sided T-test using a change of .5g/dL. Secondary endpoints will be analyzed using two-sided T-test testing for a difference between the two study arms or a Chi-square test as appropriate. Statistical significance will be determined using a p-value of 0.05.

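### Section 9.1 and the schedule give different randomization times for most women, and section 9.5 names no analysis set, so decliners may dilute the non-inferiority comparison

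*Combined protocol and SAP*

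**What the plan says.** **Timing.** Section 9.1 states: "Patients will be randomly assigned to salpingectomy or BTL at enrollment". Section 4.3 says where enrollment mostly happens: "Most subjects will be recruited and consented in the clinic setting". In the section 6.1 schedule the antepartum enrollment column is blank in the Randomization row, and the only mark is under "Delivery/ Sterilization Visit 1". Section 6.2.2 gives the order but no visit: "When patients have been enrolled in the study they will be randomized". The Précis and sections 3 and 9.2.1 likewise give only the order.

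**Women who do not go on to sterilization.** Section 5.4 lets a woman decline up to the sterilization procedure itself and adds: "We will incorporate into our analysis any patients who decline permanent sterilization after being enrolled in the study". Section 6 says that women who enroll and then "decline any form of permanent sterilization will be noted in the analysis of the results and discussed accordingly". Section 4.3 provides for a change of mind (the sentence beginning "During the final process to re-affirm consent for the study at the time of planned cesarean delivery") and calls a consented woman who becomes ineligible a screen failure. Under 6.2.2 and 7.2, sterilization goes ahead only if the woman is stable and the surgeon considers it safe. No section says how a randomized woman who is not sterilized for that reason is analyzed.

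**Analysis.** Section 9.5 states: "A 1-sided 95% confidence interval will be constructed for the difference between study arms in the mean drop in hemoglobin", with a one-sided t-test against 0.5 g/dL. It does not say who is in the comparison or by which arm. Section 5.4 counts women who completed their assigned procedure but attaches no analysis to that count.

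**The concern.** For a woman enrolled in clinic, 9.1 and the schedule give two different randomization dates, possibly far apart. Staff cannot follow both. The earlier date leaves more time for a randomized woman to change her mind.

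The trial aims to show that salpingectomy costs no more than 0.5 g/dL of extra hemoglobin drop. A woman who has the cesarean but no tubal surgery carries no information on that extra loss. An analysis of everyone by assigned arm is valid for the effect of assignment. In a non-inferiority trial, however, non-receipt unrelated to arm and bleeding pulls a true excess toward zero, and so toward the claim of safety.

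With no set named, the choice could also be made after the results are seen. Dropping untreated women is not a safe remedy on its own. Section 6.2.2 tells the surgical team the arm before surgery, so omission or crossover may depend on the arm or on bleeding.

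**Working it through.** **Inputs.** From 9.2: margin 0.5 g/dL, common SD 1.1 g/dL, one-sided alpha 0.05, 60 per arm, 80% power. A true difference of zero is not stated but is implied by the match below. The non-receipt fraction f is assumed.

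**The plan's own figure.** n per arm = 2 × [1.1 × (1.645 + 0.842) / 0.5]² = 59.9, so 60. This reproduces the plan. Power at 60 per arm is 80.1% by the normal approximation and 79.7% by noncentral t. No allowance for non-receipt is included.

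**Dilution.** Suppose a fraction f of each arm has the cesarean and both hemoglobin values but no tubal surgery, unrelated to arm and bleeding. A true excess of 0.5 among treated women becomes 0.5 × (1 − f) among all randomized.

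- Standard error = 1.1 × √(2/60) = 0.2008.
- False non-inferiority rate ≈ Φ(0.5f / 0.2008 − 1.645).
- Example, f = 0.05: Φ(0.1245 − 1.645) = Φ(−1.5205) = 0.064.

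The rates and per-protocol power in the table are by noncentral t. Per-protocol power is at zero true difference with 60 × (1 − f) per arm. The last column is from simulation at zero true difference.

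| Assumed f | Expected all-randomized difference | False-claim rate | Per-protocol n per arm | Per-protocol power | Power if both sets must meet 0.5 |
|---|---|---|---|---|---|
| 0 | 0.50 | 5.0% | 60 | 80% | 80% |
| 2% | 0.49 | 5.5% | 58.8 | 79% | 78% |
| 5% | 0.475 | 6.4% | 57 | 78% | 76% |
| 10% | 0.45 | 8.1% | 54 | 76% | 74% |

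Giving tubal ligation instead of salpingectomy to a fraction f of the salpingectomy arm dilutes the difference by the same factor.

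**If omission falls in one arm only (illustration, f = 10%).** Let tubal ligation add b g/dL to the drop and salpingectomy b + 0.5, with b assumed between 0 and 0.4.

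- Salpingectomy omitted, all-randomized: 0.9(b + 0.5) − b = 0.45 − 0.1b, which is 0.45 to 0.41.
- Ligation omitted, all-randomized: (b + 0.5) − 0.9b = 0.50 + 0.1b, which is 0.50 to 0.54.
- Per-protocol, if omitted women lost x more at the cesarean than those who went on (x assumed 0 to 1.0): 0.5 − 0.1x, which is 0.50 to 0.40, or 0.5 + 0.1x, which is 0.50 to 0.60.

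Either set can therefore be biased in either direction, which is the reason for having both.

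**The case against.** **The timing conflict may be loose wording.** Only one sentence, in 9.1, conflicts with the schedule. Re-affirmed consent and the screen-failure language in 4.3 both fit randomization at delivery, and for women enrolled on admission the two statements agree. This stands, and it is why the fix adopts the schedule's time. It does not remove the need to correct 9.1, because most women enroll in clinic.

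**Section 5.4 may mean reporting, not retention.** Its sentence sits under adherence and covers women who decline after enrollment, not after randomization. Section 6 speaks of noting and discussing. If randomization is at delivery, a woman who declines earlier has no arm. This is a fair reading, so the point is only that decliners may be kept.

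**A reader might infer that 5.4 also keeps women who become ineligible or are unstable at surgery.** The documents do not support that. The sentence in 5.4 covers only women who decline, 4.3 treats ineligible women as screen failures, and unstable women are not addressed. A woman who delivers vaginally does not fit the dilution model either, because section 6 times the postoperative sample from the cesarean and the study procedure.

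**The effect is small.** Low non-receipt is likelier if randomization is at delivery, and the inflation shown applies when the true excess sits exactly at the margin. Section 5.2 keeps women blinded to their arm until after surgery, so declining should be roughly balanced. This stands for decliners. It does not cover surgeon-driven omission or crossover, where the arm is known.

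**Conclusion.** The randomization time in 9.1 and in the schedule must be reconciled, and the primary analysis set must be named. Both gaps are in the text. The analysis-set gap remains whichever time is right, because a woman randomized at delivery can still decline or not be sterilized.

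The size is modest: a false non-inferiority rate of about 5.5% to 6.4% at 2% to 5% non-receipt, and 8.1% at 10%, against 5.0%. This rests on assumed rates, a true excess of 0.5 g/dL among treated women, non-receipt unrelated to arm and bleeding, and retained women having both hemoglobin values.

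A reader might infer that the sample size is wrong or that an all-randomized analysis is invalid. Neither follows: 60 per arm reproduces, and the all-randomized comparison is valid for the effect of assignment. The point is a low-cost improvement that should be made, not a flaw that defeats the trial.

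**What to change.** 1. **Timing.** Amend 9.1 and clarify 6.2.2 to match the schedule: randomize on the delivery admission, after consent is re-affirmed and before surgery. Women who decline or become ineligible earlier are then never randomized and appear in the participant flow only.
2. **Analysis sets.** In 9.5, make the all-randomized analysis by assigned arm primary. Add a per-protocol analysis (women who completed the assigned procedure, crossovers left out) against the same 0.5 g/dL limit.
3. **Decision rule, stated in advance.** Either conclude non-inferiority only if both analyses meet the limit, or let the all-randomized set decide and report any disagreement as a non-robust result.
4. **Reporting.** Give non-receipt and crossover by arm and reason. Align 5.4 with section 6 so that women who decline after randomization stay in their assigned arm, and state how women not sterilized for instability are analyzed.

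**Cost.** The change is wording in 5.4, 6, 6.2.2, 9.1 and 9.5, plus one analysis from data already collected.

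- Requiring both sets lowers power to about 78%, 76% or 74% at 2%, 5% or 10% non-receipt, against 80%. When non-receipt is unrelated to arm and bleeding, it also holds the false-claim rate at or below 5%, because the per-protocol test alone does.
- Under the second rule the false-claim rate in the table is unchanged. With no true difference the sets disagree by chance in about 3%, 5% or 8% of trials.
- The target of 120 randomized stays. At an assumed 5% to 10% loss before randomization, 120/0.95 = 127 or 120/0.90 = 134 consents are needed, 7 to 14 more.
- Someone able to randomize must be available at admission, as already applies to women enrolled then.

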6 STUDY PROCEDURES

Patients will be screened to be eligible in the study if they :

- 1) Desire permanent sterilization
- 2) Are scheduled for a Cesarean delivery (no emergency/'alpha' deliveries)
- 3) Are equal to or greater than 21 years of age
- 4) Have a BMI < 50

5) Have both ovaries/fallopian tubes

Patients may be screened for eligibility antenatally in the obstetrics clinic or at the time of presentation to the Family Birth Center for a non-emergent Cesarean delivery. If they meet eligibility, they will have the option to enroll in the study. A preoperative hemoglobin will be done at admission to the Family Birth center for delivery. If the patient is screened and enrolled at the time of admission to the birth center, a preoperative hemoglobin will be obtained prior to the planned cesarean delivery. All patients enrolled will have a postoperative hemoglobin obtained between 24 hours and 48 hours after the cesarean delivery and concomitant intervention procedure. Patients will be scheduled for a standard 6 weeks postpartum follow- up visit which will be reviewed. Patients who enroll in the study and then subsequently decline any form of permanent sterilization will be noted in the analysis of the results and discussed accordingly.

6.1 Schedule of Evaluations

Assessment	Antepartum Screening Enrollment	Delivery/ Sterilization Visit 1	24-hours PP Visit 2	Follow-up: 6 Week PP
Informed Consent Form	X	*X		
Demographics	X	X		
Medical History	X	X		X
Hematology		X	X	
Inclusion/Exclusion Criteria	X	*X		
Randomization		X		
Adverse Events		X	X	X

*Patients who are screened and enrolled at the time of admission to L&D will have demographic, medical history, current medications, and vital signs reviewed/collected at the time informed consent is obtained. Patients who are screened and enrolled antenatally will at the time of admission for their planned cesarean delivery.

6.2 Description of Evaluations

6.2.1 Screening Evaluation

Screening

Patients may enroll in the study any time they are determined to meet eligibility requirements (please refer to inclusion criteria in section 4.1), and before they undergo cesarean delivery.

6.2.2 Enrollment, Baseline, and/or Randomization

Enrollment

Patients will be considered for enrollment if they meet inclusion criteria (please refer to section 4.1). If a patient expresses a desire to undergo permanent sterilization to her provider at any time and will undergo a cesarean delivery then she is eligible for enrollment and the study coordinator will be contacted to introduce the study and obtain informed consent.

In the event the study coordinator is not available for consent (i.e., middle of the night, spontaneous onset of labor in a patient planning repeat cesarean for delivery), then an obstetrical provider listed in the IRB will be able to obtain consent for enrollment. The delivering provider will not obtain consent.

Randomization

- Initiation of study intervention relative to randomization: When patients have been enrolled in the study they will be randomized. The Dynamic Allocation System will be used for electronic randomization based on the stratification criteria. Outcome of randomization (arm) will be communicated to the surgical team prior to surgery and to the participant following surgery.
- After cesarean delivery has been performed and the surgeon feels it is safe to proceed with surgical sterilization procedure identified from randomization (salpingectomy vs BTL), the start and stop time of the surgical procedure will be recorded by the circulating RN or other obstetrical provider on a case report form. Total time of the procedure, in minutes, will be recorded.

Follow-up Visits (abstracted from the Electronic Medical Record)

- Visit 1 (24 hours post operatively)
 - Vital signs
 - Physical exam
 - Medications
 - Hemoglobin
 - Adverse events
- Visit 2: Scheduled post-partum exam 6 weeks post procedure.
 - Vital signs
 - Physical exam
 - Medications
 - Adverse events

Completion/Final Evaluation

Final visit will be at the patient's postpartum exam. Any untoward events from after the first 24 hours from the procedure to that time will be reviewed (i.e., blood transfusion, readmission to hospital, etc.). If the participant receives post-partum care at a local clinic, not Mayo Clinic Rochester, the study coordinator will call the participant to collect final evaluation data, using an IRB-approved telephone script.

Patients who decide to withdraw from the study will also be interviewed and reasons for this will be discussed and potential reasons explored.

